## 8.5 Follow-up Evaluations

Only participants who achieve PR or CR will have additional physical examinations repeated every 12 weeks (counting from the last day, Day 28, of the final cycle,  $\pm 2$  weeks) for up to 48 weeks or until an earlier time of PD requiring additional treatment. AEs must be reported if the AE began any time within 30 days of completing study treatment. Additionally, if a site learns of any occurrence of death, cancer or fetal anomaly that is possibly, probably, or definitely related to the drug at any time after the study is closed, the event should be reported to the AMC through Advantage eClinical within 24 hours of when the investigator learns of the event.

The following procedures should be performed during the follow-up visits:

- 8.5.1 Complete physical examination including vital signs, signs and symptoms review, toxicity, neuropathy evaluation (i.e., pain, aching, or burning in hands or feet), and performance status.
- 8.5.2 Review of interim medical history, including AIDS-defining events.

8.5.3 KS tumor assessment.

8.5.4 At a participant's final study visit, the Off-Study Summary Form will be completed.

## **9.0 MEASUREMENT OF EFFECT**

All participants will be evaluated for KS response by physical examination as described in the KS Tumor Assessment MOP within three days prior to the first day of every cycle. See [Appendix I](#) for the KS Tumor Assessment schedule.

CTEP-registered advanced practice clinicians who are non-physician investigators (i.e., NP or PA) may perform toxicity and response assessment as allowed per local licensure requirements for this study.

Any non-physician investigator performing assessments on the study must be listed in the site delegation log and be CTEP-registered and IRB approved.

### **9.1 Definition of Response**

Response and progression will be evaluated in this study as follows:

9.1.1 Complete response (CR): CR is defined as the absence of any detectable residual disease, including tumor-associated edema, persisting for at least 4 weeks. In some individuals, residual skin color changes may remain visible at one or more site(s) of lesions that were previously raised and/or red or violaceous. Suspected CR in those lesions refers only to residual macules (flat, non-palpable lesions) that are slightly darker than the surrounding normal skin. In the event such lesions are present in a participant otherwise believed to have a CR, biopsy of at least one such lesion is required in order to document the absence of malignant cells and to confirm CR. In the event that such a confirmatory biopsy is not performed and residual pigment persists, the response will be considered partial (PR). In participants in whom all detectable cutaneous disease has resolved and in whom there are no visible pigmented macules as described above, a confirmatory skin biopsy is not required. In participants known to have had visceral disease, an attempt at restaging with appropriate endoscopic or radiographic procedures should be made.

**NOTE:** To classify a response as a CR, the participant must have a CR in both the cutaneous and noncutaneous (if applicable) sites of disease and no evidence of progression as defined by the above criteria.

9.1.2 Partial response (PR): PR is defined as no new oral lesions or new or progressive visceral sites of involvement, or the appearance or worsening of tumor-associated edema (as defined in the AMC-100 MOP) or effusions or the development of five or more new cutaneous lesions in anatomic sites which were previously documented as having no evidence of cutaneous disease; AND

- A 50% or greater decrease in the number of all lesions present at entry (either total body or in the representative areas) lasting for at least 4 weeks; OR
- Complete flattening of at least 50% of all previously raised lesions (i.e., 50% of all nodular or plaque-like lesions become macules, either total body or in the representative areas) present at entry lasting for at least 4 weeks; OR
- A 50% or greater decrease in the area of the cutaneous marker lesions compared with entry lasting for at least 4 weeks; OR

- A 50% or greater decrease in the number or size of all measurable oral or visceral lesions lasting for at least 4 weeks, without evidence for progression of cutaneous lesions; OR
- Complete disappearance of non-measurable oral or visceral lesions lasting for at least 4 weeks, without evidence for progression of cutaneous lesions.

NOTE: To classify a response as PR, the participant must have at least a PR in either the cutaneous or noncutaneous sites of disease, and no evidence of progression as defined in the above criteria.

NOTE: Participants with residual tumor-associated edema or effusion who otherwise meet the criteria for CR will be classified as having a PR.

9.1.3 Stable disease (SD) is defined as any response not meeting the criteria for CR, PR, or PD.

9.1.4 Progressive disease (PD) is defined as follows:

*For participants with  $\leq 50$  cutaneous lesions*

PD is defined as any one or more of the following:

- $\geq 25\%$  increase in the area of the cutaneous marker lesions compared to entry or best response;
- $\geq 25\%$  increase in the total lesion count, or a minimum of five new lesions, whichever is greater, compared with entry or best response;
- $\geq 25\%$  increase in the number of raised lesions, or a minimum of five new raised lesions, whichever is greater, compared with entry or best response.

NOTE: There are body sites where disease is particularly difficult to evaluate, and a few new lesions may be counted in spite of the fact that a participant is not actually progressing. For example, lesions of the foot, particularly those that are flat, are difficult to evaluate because their intensity may vary based on how much edema is present, how much the person walked the day before, how long his/her feet have been in a dependent position prior to the physical exam.

*For participants with  $> 50$  cutaneous lesions*

PD is defined as any one or more of the following:

- $\geq 25\%$  increase in the area of the cutaneous marker lesions compared to entry or best response;
- $\geq 25\%$  increase in the total number of lesions in the prospectively defined anatomic sites containing representative lesions;
- a total of five new lesions in anatomic sites that were previously documented as having no evidence of cutaneous disease,
- $\geq 25\%$  increase in the number of raised lesions in the prospectively defined anatomic sites containing representative lesions (minimum of five raised lesions if there are very few raised lesions, for example  $< 8$ ) whichever is

greater. Photographic documentation of “gross” or significant progression, particularly in areas that were not being followed, will be of particular value.

9.1.5 Noncutaneous progression (PD): Noncutaneous PD includes new oral or visceral sites of involvement or progression of oral or visceral disease or the development of new or increasing tumor-associated edema or effusion that interferes with the participant’s normal activities lasting for at least two consecutive evaluations. Progressive oral or visceral disease, for measurable and evaluable disease, should be analogous to cutaneous KS response criteria.

Progressive edema is defined as the following:

- An increase in non-pitting/woody edema in an upper or lower extremity associated with an increase in limb circumference of at least 3 cm from entry or best response, sustained for at least two consecutive evaluations, and measured at a fixed point on the extremity with respect to a bony landmark (e.g., 10 cm below the lower border of the patella); AND/OR
- New appearance of non-pitting/woody edema in an extremity where none was previously present, sustained for at least two consecutive evaluations; AND/OR
- New or worsening edema in a non-extremity site (e.g., periorbital, genital) that interferes with function and is sustained for at least two consecutive evaluations.

9.1.6 Recurrent disease

Recurrent disease is defined as the appearance of tumor following documentation of a complete remission.

9.1.7 Time to response

Time to response is defined as time from the first dose of chemotherapy until documentation of first response.

9.1.8 Time to progression

Time to progression is defined as time from initiation of chemotherapy to documentation of first progression.

9.1.9 Response duration

Response duration is defined as the time from first documentation of response to documentation of first progression.

## 10.0 STATISTICAL CONSIDERATIONS

### 10.1 Study Design/Endpoints

#### Primary endpoints

- Overall response rate
- Complete response rate
- Proportion of participants who experience toxicities of Grade 3 or higher

#### Secondary endpoints

- Changes in CD4 counts
- Changes in HIV viral loads

#### 10.1.1 Statistical rationale

The sample size is based on determining if pomalidomide administered as monotherapy has sufficient efficacy (overall response rate (ORR)  $\geq 30\%$ ) to merit consideration of further clinical development in this clinical setting, and is tolerable.

#### 10.1.2 Statistical power calculation

To test the null hypothesis that the ORR = 0.10 against the alternative that it is 0.30 with pomalidomide monotherapy at the one-sided 0.10 significance level with power of 0.90 will require 30 participants. The following stopping rule is based on stopping when the probability of observing more than x dose-limiting toxicities (DLTs) in the first cycle, as defined in [Section 4.2](#), is less than 0.05 with an underlying first cycle DLT rate of 0.10.

Since the enrollment is planned to close at the end of 2023, the target number of enrollment (30 participants) may not be achieved. It is expected that 26 participants will be able to be enrolled before study enrollment closes. As an illustration of statistical power based on the assumption that the null hypothesis that the ORR = 10% against the alternative that it is 30% with pomalidomide monotherapy at the one-sided 10% significance level, statistical power of 87.5% can be achieved with 26 participants. The following stopping rule is based on stopping when the probability of observing more than x DLTs in the first cycle, as defined in [Section 4.2](#), is less than 5% with an underlying first cycle DLT rate of 10%.

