#### **I. Scientific and Substantive Changes**

#	Section	Comments
1.	Protocol Synopsis 2.3 3.3 Table 12-1	
The accrual targets (overall and by ethnic category), study design and rationale, and sample size were updated to reflect the expected enrollment of 26 participants instead of the originally planned 30 participants.
 
The number of participants to be entered has been reduced from the originally planned 30 to 26 because Celgene, the donor of the study drug, requires that the last participant begin on study treatment no later than December 1, 2023. The revised sample size will provide only a slightly reduced statistical power (87.5% vs 90%) to test the null hypothesis that the ORR = 10% against the alternative that it is 30% with pomalidomide monotherapy at the one-sided 10% significance level.

2.	10.1.2	The statistical power calculation was updated to reflect the expected enrollment of 26 participants instead of the originally planned 30 participants.
3.	Table 4-1 10.1.3 Table 10-1 Table 10-2	Due to the expected enrollment of 26 participants instead of the originally planned 30 participants, the table describing the criteria for dose reduction, the table describing stopping rules for dose-limiting toxicity, and the table describing stopping rules for hematologic and non-hematologic toxicity were updated to remove the stopping rules for 28-30 participants. In addition, the stopping rule for dose-limiting toxicities for 21-27 participants was adjusted to 21-26, and the stopping rule for hematologic and non-hematologic toxicity for 27 participants was removed.

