### 2.3 Study Design and Rationale

This is an open label, Phase II study of orally administered pomalidomide in participants with AIDS-associated KS in sub-Saharan Africa.

Pomalidomide monotherapy will be evaluated in 26 participants, who will be enrolled at a daily oral dose of 4 mg daily for 21 days of a 28-day cycle. This dosage may be de-escalated to 3 mg daily for 21 days of a 28-day cycle if  $\geq$  Grade 2 toxicities are observed.

Pomalidomide will be considered for future development in this setting, either as a single agent or in combination with other anti-KS therapy, if the following conditions are met:

- An overall response rate of at least 30% is achieved; and,
- Either of the doses tested are tolerable, defined as no more than six participants showing  $\geq$  Grade 3 toxicities.

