#### 10.1.4 Statistical analysis plan

The binomial proportion and its 90% one-sided exact confidence interval will be

used to estimate the overall response rate, the complete response rate, and the proportion of participants who experience a Grade 3 or higher toxicity. If the lower bound of the 90% exact confidence interval for the overall response rate is  $> 0.10$ , then the null hypothesis will be rejected.

Changes in CD4 counts and HIV viral load will be evaluated using generalized estimating equations.

To assess the effect of pomalidomide treatment on serum cytokine levels, general estimating equations (GEE) will be used to evaluate changes in cytokine levels from baseline. Logistic regression analyses will be used to determine if changes in cytokine levels from baseline are associated with clinical response.

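### Section 10.1.2 states 87.5% power at 26 participants; the exact test in 10.1.4 has 83.7%, and sections 2.3 and 10.1.1 do not say whether 30% is an observed threshold

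*Combined protocol and SAP*

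**What the plan says.** Section 10.1.2 first gives the earlier design: a test of ORR 10% against 30% "at the one-sided 0.10 significance level with power of 0.90 will require 30 participants". It then explains that enrollment will close before 30 is reached: "It is expected that 26 participants will be able to be enrolled before study enrollment closes". The power for that number is introduced with "As an illustration of statistical power based on the assumption" and given as "statistical power of 87.5% can be achieved with 26 participants", for the same hypotheses and level. No test or formula is named.

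The summary of changes uses the same pair of figures to support the smaller trial: "The revised sample size will provide only a slightly reduced statistical power (87.5% vs 90"%).

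Section 10.1.4 fixes the analysis as the binomial proportion with an exact one-sided 90% confidence interval. The decision rule opens "If the lower bound of the 90% exact confidence interval for the overall response rate is" and goes on to require a value above 0.10. It gives no critical number of responders and no attained type I error.

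Section 2.3 begins "Pomalidomide will be considered for future development in this setting" and lists two conditions. The first is "An overall response rate of at least 30% is achieved"; the second is an observed count of participants with toxicity. Section 10.1.1 describes sufficient efficacy as an ORR of 30% or more and bases the sample size on it. Section 1.1.1 states 30% as a hypothesis about the true rate.

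**The concern.** There are two points.

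First, a stated power should be the power of the test that will be run. The planned test is exact, and with 26 binary outcomes its properties are coarse, so an approximate figure can be several points off. Here the figure also supports the statement that cutting the sample size costs little.

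Second, the plan has a test against 10% and a 30% criterion, and nothing connects them. If 30% is an observed threshold, a trial can reject the null and still fail the condition for development. If 30% is only the alternative used for sizing, the same result meets the efficacy criterion. The trial is open label and KS response is assessed before every cycle (sections 2.3 and 8.3), so an unsettled criterion could be interpreted after responses are known.

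**Working it through.** **Inputs.** p0 = 0.10, p1 = 0.30, one-sided level 0.10, n = 26 and n = 30 (section 10.1.2); exact one-sided 90% lower bound, reject if above 0.10 (section 10.1.4).

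**Where 87.5% might come from.** The one-sample normal approximation is

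power = Φ[(p1 − p0 − z·√(p0(1−p0)/n) − c) / √(p1(1−p1)/n)],

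with c = 0, or c = 1/(2n) for a continuity correction. At n = 26 the two standard errors are √(0.09/26) = 0.0588 and √(0.21/26) = 0.0899.

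| z | c | n = 26 | n = 30 |
|---|---|---|---|
| 1.282 (one-sided 10%) | 0 | 91.7% | 94.0% |
| 1.645 (one-sided 5%) | 0 | 87.46% | 90.6% |
| 1.282 | 1/(2n) | 87.9% | 91.2% |
| 1.645 | 1/(2n) | 82.5% | 86.7% |

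For row 2 at n = 26: (0.20 − 1.645 × 0.0588)/0.0899 = 1.149, and Φ(1.149) = 0.8746. That is the closest match, but it uses a 5% level, not the stated 10%. Row 3 uses the stated level and comes near. The documents do not show which was used.

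**The planned test at n = 26.** The exact lower bound is 0.0966 for 5/26 and 0.1260 for 6/26, so 6 responders are needed. With X ~ Bin(26, p):

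- Type I error: P(X ≥ 6 | 0.10) = 0.0399
- Power: P(X ≥ 6 | 0.30) = 0.8374
- Excess of the stated figure: 87.5 − 83.7 = 3.8 points

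A cut-off of 5 would give type I error 0.1118, above the 10% level. Reading the interval as two-sided 90% gives a bound of 0.1056 at 6/26, so the cut-off and the power do not change.

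**The same rule at other n.**

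| n | Responders needed | Type I error | Power at 30% |
|---|---|---|---|
| 24 | 5 | 8.5% | 88.9% |
| 25 | 5 | 9.8% | 91.0% |
| 26 | 6 | 4.0% | 83.7% |
| 27 | 6 | 4.7% | 86.4% |
| 30 | 6 | 7.3% | 92.3% |

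Loss from n = 30 to n = 26: stated 90.0 − 87.5 = 2.5 points; exact 92.3 − 83.7 = 8.6 points.

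**How much of the 8.6 points is sample size?** Interpolating between adjacent cut-offs (a randomised test) puts both sizes at one type I error:

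- At 7.32%: for n = 26 the weight on 5 responders is (0.0732 − 0.0399)/(0.1118 − 0.0399) = 0.463, so power is 0.8374 + 0.463 × (0.9267 − 0.8374) = 0.8788. The loss is 92.3 − 87.9 = 4.5 points (before rounding).
- At 3.99%: for n = 30 the weight on 6 responders is (0.0399 − 0.0258)/(0.0732 − 0.0258) = 0.296, so power is 0.8405 + 0.296 × (0.9234 − 0.8405) = 0.8650. The loss is 86.5 − 83.7 = 2.8 points.
- At exactly 10%: 93.6% against 91.2%, a loss of 2.4 points.

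The remainder comes from the cut-off staying at 6 while n falls, which makes the rule stricter.

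**The 30% criterion.** 7/26 = 26.9% and 8/26 = 30.8%, so an observed 30% needs 8 responders.

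| True ORR | P(8 or more) | P(6 or 7) |
|---|---|---|
| 30% | 54.0% | 29.8% |
| 35% | 74.0% | 19.5% |
| 40% | 87.8% | 10.0% |
| 47% | 97.0% | 2.7% |
| 73% | about 100% | about 0 |

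At ORR 10%, P(8 or more) = 0.3%. The range 35% to 47% is the span of thalidomide partial response rates cited in section 2.1.3, and 73% is the pomalidomide rate cited in section 2.2.1.

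**The case against.** The strongest reply is that 87.5% is offered as an illustration for an expected enrollment, and that planning by approximation and analysing exactly is common. A continuity-corrected approximation at the stated level gives 87.9% and 91.2%, near both stated figures. This explains how such a figure could arise, but the section gives it as the power at 26, and the planned test does not have that power.

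It can also be said that 8.6 points overstates the cost of losing four participants, because exact power moves in a sawtooth: at n = 25 it is 91.0%. This largely stands. At a common type I error the loss is between 2.4 and 4.5 points, so 8.6 describes the change in the rule as it will operate, including its stricter error rate, and should be quoted with both error rates.

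Third, the number was set by the drug donor's deadline for the last participant to start, not by power, and the rejection rule is explicit. True: no test or sample size changes. The stated figure still needs correcting.

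On the 30%, section 2.3 says only that the drug will be considered if the conditions are met, not only if, and a test against 10% can coexist with a separate threshold of interest. That stands too: this is an ambiguity, not an error. The observed reading is the more natural one beside a participant count, but sections 1.1.1 and 10.1.2 use 30% as a true rate.

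**Conclusion.** The concern holds. For the test in section 10.1.4 at n = 26, 6 responders are needed, type I error is 4.0%, and power at ORR 30% is 83.7%. The 87.5% in section 10.1.2 is 3.8 points too high, and its origin is not established. On the exact basis, power goes from 92.3% at n = 30 to 83.7% at n = 26, with type I error going from 7.3% to 4.0%. The test itself is valid and 83.7% is still reasonable power.

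The meaning of 30% in sections 2.3 and 10.1.1 is unresolved. It matters near the design alternative, where 6 or 7 responders occur 29.8% of the time and the observed threshold would be met only 54.0% of the time. It matters little at a true rate of 47% or above.

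These figures assume 26 participants in the denominator and independent responses with a common rate. Because 26 is an expected number, a different final n changes the cut-off and the power, as tabulated.

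**What to change.** 1. In section 10.1.2, replace 87.5% with the properties of the section 10.1.4 test at n = 26: reject at 6 or more responders, type I error 4.0%, power 83.7% at ORR 30%. Put the n = 30 comparison on the same basis: 6 or more, 7.3%, 92.3%. Giving cut-off, error and power together keeps the fall in power from being read as the effect of sample size alone.

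2. In sections 2.3 and 10.1.1, say which meaning of 30% applies.
   - If it is an observed threshold: add that 8 of 26 are needed, that this is met with probability 54.0% at ORR 30% and 0.3% at ORR 10%, and that 6 or 7 responders will be reported as null rejected, 30% condition not met.
   - If it is only the design alternative: name rejection of ORR 10% under section 10.1.4 as the efficacy criterion, and disclose whether response data had been seen when this was clarified.

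Sections 10.1.4 and 1.1.1 need no change. The cost is text only: a lower stated power, a larger stated loss from n = 30, and possibly a statement that responses were already known. Sample size, data collection, test and analysis are unchanged.

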#### 10.1.3 Stopping Rules

**Table 10-1. Stopping Rules for Dose-limiting Toxicity**

N	More Than X Participants with DLTs
7-8	2
9-14	3

15-20	4
21-26	5

The study team will monitor trial safety and the safety stopping rule using the procedures outlined in the DMSP. The AMC Data and Safety Monitoring Board (DSMB) will perform an annual review of trial safety to evaluate whether DLTs have occurred and that the safety stopping rule has been followed appropriately. Accrual will not be paused for these reviews because they are confirmatory to the study team's process, unless the safety rule is invoked by the study team's review.

**Table 10-2. Stopping Rules for Hematologic and Non-Hematologic Toxicity**

Stop if the number of cycle 1 $\geq$ Grade 3 hematologic toxicities exceeds X OR the number of cycle 1 $\geq$ Grade 3 non-hematologic toxicities exceeds Y		
N	X (hem)	Y (non-hem)
7	6	2
8	6	2
9	7	3
10	8	3
11	8	3
12	9	3
13	9	3
14	10	3
15	11	4
16	11	4
17	12	4
18	12	4
19	13	4
20	14	4
21	14	5
22	15	5
23	15	5
24	16	5
25	17	5
26	17	5

The stopping rule for hematologic toxicities is based on probability of observing  $> x \geq$  Grade 3 hematologic toxicities  $< 0.05$  if the underlying rate of  $\geq$  Grade 3 hematologic is 0.50.

The stopping rule for non-hematologic toxicities is based on probability of observing  $> x \geq$  Grade 3 non-hematologic toxicities  $< 0.05$  if the underlying rate of  $\geq$  Grade 3 hematologic is 0.10.

